9.3. Subgroup Analyses

Analyses for preliminary efficacy and exploratory analyses for QoL will be done in all patients and in the following subgroups of patients, if a sufficient number of patients are evaluable in each subgroup:

- Enzalutamide and/or abiraterone naïve, had prior treatment with abiraterone, or are enzalutamide resistant.
- ARV7 positive or ARV7 negative circulating tumor cells at baseline
- GR+ or GR- negative circulating tumor cells at baseline
- GR+ or GR- biopsy at baseline/screening
- Line of therapy
- Systemic antagonism of cortisol activity

10. Safety Analyses

All safety analyses, except evaluation of DLTs, will use data from the Safety population. Relevant safety data collected through the course of the study on eCRF pages, including adverse events, deaths, clinical lab assessments, physical examination, vital signs, ECOG performance status, and 12-Lead electrocardiogram, will be presented in data listings and summary tables.

10.1. Adverse Events

Per protocol, adverse events will be collected from the time of signing the ICF until 30 days after the last dose of exicorilant or enzalutamide. Illnesses present before the patient signs the ICF will be considered pre-existing conditions and documented on the medical history eCRF.

Pre-existing conditions that worsen during the study will be entered on the AE eCRF. Adverse events that occur after the first dose of exicorilant through 30 days after administration of the final dose of study treatment will be considered treatment-emergent adverse events (TEAEs). Adverse events reported more than 30 days after the last dose of study treatment will be considered post-treatment AEs.

Incidence of TEAEs will be listed and summarized using the current version of Medical Dictionary for Regulatory Activities (MedDRA v20.1 or later) by system organ class and preferred term. A hierarchical listing will display the MedDRA system organ classes represented in the data, and within each system organ class, the listing will display each unique preferred term ordered alphabetically. At each level of summation of system organ class and preferred term, patients reporting more than one AE will only be counted once. Similarly, multiple incidences of the same AE for each patient will be reported only once at the maximum severity. If relationship to study drug is missing, the adverse event will be counted as related. Adverse event listings will show missing relationship as missing.

All AEs (whether TEAEs or not) will be listed in a listing by treatment group and individual patient, including dates of onset and resolution, whether ongoing, or serious, CTCAE toxicity grade, action taken and relationship to study drug. Serious TEAEs and TEAEs that lead to withdrawal from exicorilant or enzalutamide will be listed separately.

Summary tables will be provided for:

- Overall summary of TEAEs.
- TEAEs occurring 10% or higher in the Safety population by preferred term and CTCAE grade.
- All TEAEs.
- Grade 3 or greater TEAEs.
- TEAEs related to exicorilant.
- TEAEs related to enzalutamide.
- Grade 3 or greater TEAEs related to exicorilant.
- Grade 3 or greater TEAEs related to enzalutamide.
- Grade 3 or greater TEAEs related to exicorilant and enzalutamide.
- Serious TEAEs
- TEAEs leading to withdrawal of exicorilant.
- TEAEs leading to withdrawal of enzalutamide.
- TEAEs requiring dose interruption or reduction of exicorilant.
- TEAEs requiring dose interruption or reduction of enzalutamide.
- TEAEs requiring dose interruption or reduction of exicorilant and enzalutamide.

- AEs occurring only during enzalutamide lead-in period.

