In accordance with the study design, subjects in the MAD part of the study took part in 3 study epochs: 15 mg pioglitazone alone; randomized study treatment alone; and randomized study treatment with a single concomitant dose of 15 mg pioglitazone. For the purpose of assessing the safety of CORT125281, the focus of this section is on treatment-emergent adverse events (TEAEs) occurring during the period with randomized study treatment alone.

Treatment-related gastrointestinal disorders and musculoskeletal and connective tissue disorders were reported only by subjects treated with CORT125281 and with a generally increasing incidence with dose. Within the system organ class (SOC) gastrointestinal disorders, the preferred terms nausea, abdominal discomfort, and diarrhea were reported by $\geq 10\%$ of subjects treated with CORT125281, with single reports of abdominal pain, constipation, dyspepsia, gastroesophageal reflux disease, mouth ulceration and vomiting. Within the SOC musculoskeletal and connective tissue disorders, back pain and neck pain were reported, with a single report of joint stiffness. Ear and labyrinth disorders (ear pain, tinnitus, ear discomfort, and ear congestion) and nervous system disorders (headache, somnolence, and dizziness) were reported by generally similar proportions of subjects across all treatment groups including placebo.

In total, 2 TEAEs were graded severe in intensity: abdominal pain in a subject treated with CORT125281, 240 mg BID and back pain in a subject treated with CORT125281, 360 mg QD after concomitant pioglitazone.

CORT125281-601

In the current study, a total of 14 patients with mCRPC have been enrolled to 3 sequential dose-finding cohorts to evaluate CORT125281 BID under fasting conditions in combination with

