enzalutamide 160 mg QD. Twelve patients have received CORT125281 in combination with enzalutamide, and 2 patients discontinued the study during the enzalutamide lead-in and did not receive CORT125281. In Cohort 1, two patients received CORT125281 180 mg BID with enzalutamide. Both patients experienced dose-limiting toxicities (DLTs), including Grade 3 fatigue (n=1), and the concurrent SAEs of Grade 3 fatigue and Grade 3 musculoskeletal pain (n=1); thus CORT125281 180 mg BID was deemed intolerable. A lower dose (CORT125281 140 mg BID) was evaluated in Cohort 2. In Cohort 2, 1 of 3 patients experienced a DLT (SAE of Grade 3 acute pancreatitis). After the third patient enrolled to Cohort 2, an interim assessment of PK and safety was conducted. Based upon the absence of a clinically significant drug interaction of CORT125281 on enzalutamide exposure, enrollment to the subsequent cohort was initiated to further evaluate the CORT125281 140 mg BID dose level without the enzalutamide lead-in. Seven patients have been enrolled to Cohort 3. One patient was not evaluable for DLTs due to disease progression during Cycle 1. Of the 6 remaining patients, no DLTs were observed and the dose was considered tolerable.

Twelve patients (100%) who have received at least 1 dose of CORT125281 in combination with enzalutamide reported greater than 1 TEAE. Five patients (42%) reported TEAEs of Grade 3 or greater considered related to CORT125281; the most frequent TEAE of Grade 3 or greater was fatigue (n=2; 17%). An alternative schedule (once daily [QD] dosing of CORT125281) is planned to optimize the biologically active dose prior to proceeding to the Phase 2 expansion cohorts.

CORT125281-602

In accordance with the study design, 6 healthy subjects received a single oral dose of [¹⁴C]-CORT125281 360 mg (6 × 60-mg capsules). No TEAEs were reported in this study.

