6.2. Safety Analysis Population

Safety Population: All patients who received at least 1 dose of exicorilant. All safety analyses, except evaluation of DLTs, will be based on the Safety Population.

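### The table of adverse events in the enzalutamide lead-in is limited to patients who later took exicorilant, so it describes 5 of the 7 patients in the lead-in cohorts

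*SAP*

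**What the plan says.** The list of summary tables in SAP Section 10.1 ends with "AEs occurring only during enzalutamide lead-in period". No population is named for that table, so the general rule at the start of Section 10 applies: "All safety analyses, except evaluation of DLTs, will use data from the Safety population". The sentence after that rule extends it to data listings as well as summary tables. SAP Section 6.2 defines the Safety Population as "All patients who received at least 1 dose of exicorilant", and protocol Section 9.2 agrees.

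Protocol Section 1.3.2.1 reports on Segment 1 as of 18 February 2020 (CORT125281 is exicorilant): "a total of 14 patients with mCRPC have been enrolled to 3 sequential dose-finding cohorts"; "Twelve patients have received CORT125281 in combination with enzalutamide"; and "2 patients discontinued the study during the enzalutamide lead-in and did not receive CORT125281".

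Three other provisions bear on the point:
- Protocol Section 5 counts enzalutamide given under the protocol as study treatment, and AEs are collected from signature of consent (protocol 6.3.5 and 8.1.2, SAP 10.1).
- SAP Sections 7.2, 10.1 and 13 start the treatment-emergent period at the first exicorilant dose.
- The separate listings in SAP 10.1 of serious events and of events leading to withdrawal are confined to treatment-emergent AEs (TEAEs).

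**The concern.** A table meant to describe a treatment period should count everyone who entered the period. This one counts only those who completed it and then took the next drug. An AE that caused a patient to leave during the lead-in cannot appear, by construction, so for events of that kind any bias runs in one direction only.

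The table carries some weight because it is the only planned summary of lead-in AEs. With the treatment-emergent period starting at exicorilant, events that begin in the lead-in fall outside every TEAE table. A reader trying to separate enzalutamide toxicity from combination toxicity would naturally turn to it: both treated patients in Cohort 1 had Grade 3 fatigue as a DLT, and protocol Section 1.6 names fatigue as the most common AE of enzalutamide. What is at stake is complete safety reporting for patients who took study treatment under consent.

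**Working it through.** **Inputs** (protocol 1.3.2.1 unless noted)
- Enrolled in Segment 1: 14.
- Cohort 1: "In Cohort 1, two patients received CORT125281 180 mg BID with enzalutamide", so 2 treated.
- Cohort 2: "In Cohort 2, 1 of 3 patients experienced a DLT", so 3 treated.
- Cohort 3: 7 enrolled, with no enzalutamide lead-in (also SAP 8.8).
- Left during the lead-in without exicorilant: 2.

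**Reproducing the protocol's counts.** Treated = 2 + 3 + 7 = 12. Not treated = 14 − 12 = 2. Both match the protocol.

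**Patients in the lead-in cohorts.** 14 − 7 = 7. The protocol does not print this number. As a check, 2 + 3 treated plus 2 who left is also 7.

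**Patients in the planned table.** Lead-in patients in the Safety Population = 2 + 3 = 5. Excluded = 7 − 5 = 2, which is 2/7 = 28.6% of lead-in patients and 2/14 = 14.3% of those enrolled.

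**Whether another population holds the 2 patients.**
- ITT (SAP 6.1) needs a dose of the combination.
- DLT-Evaluable (SAP 6.3) needs exicorilant.
- PK-Evaluable (SAP 6.4) and Response-Evaluable (protocol 9.2) are subsets of the Safety Population.

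None does. The problem is confined to Segment 1: the Expansion Phase food-effect lead-in uses exicorilant itself, so those patients enter the Safety Population with their first dose.

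**Effect on the table, for an AE that ended the lead-in** (Clopper-Pearson 95% intervals, the SAP's binomial method)

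| Set | Events/patients | Percent | 95% CI |
|---|---|---|---|
| Planned table | 0/5 | 0% | 0% to 52.2% |
| All 7, neither left for an AE | 0/7 | 0% | 0% to 41.0% |
| All 7, one left for an AE | 1/7 | 14.3% | 0.4% to 57.9% |
| All 7, both left for an AE | 2/7 | 28.6% | 3.7% to 71.0% |

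The planned table returns the first row whichever of the other three is true.

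**Why a population flag is not enough for two listings.** The serious and withdrawal listings omit lead-in events because they are limited to TEAEs. That holds even for the 5 patients who continued. Changing the population alone would leave these listings as they are. Protocol 9.5.6 plans listings of serious AEs and of AEs leading to study withdrawal without that limit.

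**The case against.** The strongest reply is that little is lost. Disposition (SAP 8.1) covers all enrolled patients, lists those who discontinue, and gives AE and death among the reasons. SAP 10.1 promises a listing of all AEs, treatment-emergent or not, and SAP 10.2 a listing of all deaths; neither names a population. The exicorilant-based Safety Population is deliberate, is the same in both documents, and suits the TEAE tables. The change to the treatment-emergent period is disclosed in SAP 13. The stated uses of the lead-in are enzalutamide pharmacokinetics and drug interaction (protocol 5.4.1, 6.6) and change in PSA and circulating tumor cells (9.5.5); no passage plans to read combination toxicity against lead-in AEs. For a within-patient comparison, the 5 patients seen in both periods are a coherent set.

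Most of this stands, and it limits the point. A reader might infer that the 2 patients disappear from every safety output, or that a death among them would be reported nowhere. The documents do not support that: disposition would show a death or an AE given as the reason for leaving, and the wording of the all-AE and death listings is ambiguous rather than excluding. A reader might also infer that an AE probably made them leave, and hence that the table does flatter the lead-in. No reason is given. Disease progression or withdrawal of consent is equally open, and protocol 5.4.1 lets patients whose lead-in toxicity requires dose modification continue on modified enzalutamide.

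The reply does not rescue the lead-in table. Disposition gives no AE term, grade or seriousness. The all-AE and death listings sit under the general rule of Section 10, which points to exclusion, and where the SAP means all enrolled patients, as in 8.1, it says so.

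**Conclusion.** The point holds for the lead-in AE table. Under the SAP's stated rule it covers 5 of 7 patients in the lead-in cohorts and leaves out the 2 (28.6%) who left during the period it describes. Those 2 have no assured place in any AE output. For an AE that ended the lead-in, the table shows 0/5 where the figure over all 7 lies between 0/7 and 2/7; the documents do not allow a narrower statement.

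This rests on three things: the 18 February 2020 cut (SAP 8.8 still names the same three cohorts); the derived count of 7; and the assumption that both patients took at least one enzalutamide dose before leaving, which the protocol's wording implies but does not state.

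DLTs are counted from the first exicorilant dose, so no conclusion on DLTs, the maximum tolerated dose or the recommended dose depends on this table. It is an inexpensive correction to the completeness of safety reporting.

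**What to change.** Make three changes to the SAP and keep the exicorilant-based Safety Population for the TEAE tables.

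1. Define an enzalutamide-treated set of all patients with one or more doses of on-study enzalutamide in the lead-in, and make it the denominator of the lead-in AE table.
2. State in 10.1 and 10.2 that the all-AE and death listings cover every patient given one or more doses of on-study enzalutamide or exicorilant.
3. Widen the separate listings of serious events and of events leading to withdrawal from TEAEs to AEs, with a marker for events that began in the lead-in.

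The cost is one extra population flag, a few lines of text and slightly longer listings. No new data are needed, because AEs are already collected from consent.

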10.2. Deaths

All deaths, causes of death, and whether an autopsy report is available will be listed and summarized.

10.3. Clinical Laboratory Results

Clinical laboratory tests will be performed according to the SoA and samples analyzed at local laboratories. Results for hematology, serum chemistry, coagulation, urinalysis, PSA measurement, thyroid function, Hepatitis Serology and HIV, along with abnormal values where relevant, and normal ranges in reported and SI units will be presented in data listings. For list of laboratory tests, see Protocol Table 11.

Summaries of actual values and changes from baseline will be presented by treatment regimen dose group, by arm and overall, for each parameter and assessment time point. Change from Baseline will be calculated as the post-baseline minus the baseline measurement.

For parameters that can be graded using the NCI-CTCAE, shift tables that summarize counts and percentages of patients by severity grade at baseline and worst post-baseline result will also be constructed.

10.4. Vital Signs

At designated visits, vital signs will be recorded and will include weight, blood pressure, heart rate, respiration rate, and temperature. Listing of all vital signs data along with height, and derived BMI will be provided. Additionally, data will be summarized by treatment regimen dose group/arm, and overall, using descriptive statistics at baseline, each study evaluation, and change from baseline to each post-baseline evaluation. If either value is missing, the observation will not be included in the summary statistics.

10.5. 12-Lead Electrocardiogram

12-lead ECG (triplicate) is performed before dosing and approximately 2 hours post-dose (± 10 minutes) on Cycle 1 Day 1 and Cycle 1 Day 15 (for all patients) and Cycle 3 Day 1 (for patients in Dose-Determination Phase Segment 1 only). At scheduled visits, 12-Lead ECGs will be obtained in triplicate (3 recordings made at intervals of at least 2 minutes apart) and presented in data listings. The Investigator or Sub-Investigator (physician) will be responsible for review and interpretation of the results and determining whether the ECG is normal, abnormal clinically significant, or abnormal not clinically significant. All recorded results will be included in a listing, and worst result of the triplicate readings at each visit will be summarized for each treatment arm as shift from Baseline.

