 - b. Acute coronary syndromes (including unstable angina), coronary angioplasty, stenting, or bypass grafting within the past 6 months prior to enrollment, Class III or IV heart failure as defined by the New York Heart Association functional classification
 - c. Recent history of or risk factors for torsades de pointes, including marked baseline prolongation of QT interval (eg, repeated demonstration of a corrected QT [QTc] interval >450 milliseconds using Fridericia's formula [QTcF] or need for concomitant medication associated with QT prolongation; refer to <https://www.crediblemeds.org/>)
 - d. Uncontrolled hypertension: Sustained systolic blood pressure ≥ 180 mmHg or diastolic blood pressure ≥ 100 mmHg; patients will be considered eligible if hypertension is treated and controlled during Screening
 - e. Active infection requiring IV anti-infective treatment
 - f. Human immunodeficiency virus (HIV) or current chronic/active infection with hepatitis C virus or hepatitis B virus, including:
 - i. Patients with chronic or active hepatitis B as diagnosed by serologic tests are excluded from the study. In equivocal cases, hepatitis B or C polymerase chain reaction may be performed and must be negative for enrollment.
 - g. Active autoimmune disease requiring systemic treatment
 - h. Alcohol or other substance abuse or cirrhosis
9. Received herbal products or alternative therapies that may decrease PSA levels or that may have hormonal anti-prostate cancer activity (eg, saw palmetto, PC-SPES, PC-HOPE, St. John's wort, selenium supplements, grape seed extract) within 21 days of study treatment initiation or plans to initiate treatment with these products/alternative therapies during the entire duration of the study.
10. Received systemic GCs within 21 days prior to the first dose of CORT125281, or requirement for chronic or frequently used systemic or inhaled GCs for medical conditions (eg, rheumatoid arthritis, immunosuppression after organ transplantation). Short courses (≤ 5 days) for non-cancer-related reasons are allowed if clinically required (such as prophylaxis for CT).
11. Concurrent therapy with strong inhibitors or inducers of CYP3A4 or CYP2C8 or with sensitive substrates of CYP3A4, CYP2C9, or CYP2C19. For patients currently receiving strong CYP3A4 or CYP2C8 inducers, a minimum wash-out period of 21 days

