9.5.6 Safety Analysis

Safety analyses will be conducted on the Safety Population.

The incidence of TEAEs, defined as AEs occurring after the first dose of study treatment through 30 days after the final dose of study treatment, will be summarized using Medical Dictionary for Regulatory Activities (MedDRA) by SOC and preferred term. Treatment-emergent AEs will be further summarized by severity and relationship to study treatment. For each patient, if multiple incidences of the same AE occur, the maximum severity reported will be used in summaries.

All AEs (whether TEAEs or not) will be listed by individual patient, including information regarding onset, duration, severity, and relationship to study treatment (CORT125281 or enzalutamide). Serious AEs and AEs that led to withdrawal from the study will be listed by individual patient.

The following adverse events will be summarized separately: AEs leading to withdrawal of study treatment (CORT125281 or enzalutamide), dose reduction or interruption, Grade 3 or greater AEs, and SAEs.

All deaths and causes of deaths will be summarized and listed.

Clinical laboratory test results, vital sign measurements, and abnormal ECG values will be summarized overall and for each treatment regimen dose group by parameter, visit, and time

point using descriptive statistics, to include the change from baseline values. Shift tables will be constructed that describe changes from baseline to the end of treatment.

By-patient safety listings will be provided.

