4.2. Secondary Endpoints

4.2.1. Secondary Safety Endpoints

The safety and tolerability will be assessed by evaluating the following endpoints:

- Incidence of adverse events (AEs), serious AEs (SAEs), treatment-related AEs, AEs by severity, deaths
- Discontinuations of treatment and study withdrawal due to AEs
- Dose interruptions and reductions due to AEs
- Change from Baseline in clinical laboratory tests
- Change from Baseline in vital signs (including blood pressure, heart rate)
- Shift from Baseline in 12-Lead Electrocardiogram (ECG)
- Change from Baseline in Eastern Cooperative Oncology Group (ECOG) performance status

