7.2. Definitions

Study day: Study day will be calculated in reference to the date of the first dose of exicorilant. For assessments conducted on or after the date of the first dose of exicorilant, study day will be calculated as (assessment date - date of first dose of study drug + 1). For assessments conducted before the date of the first dose of exicorilant, study day is calculated as (assessment date - date of first dose of study drug). There is no study day 0.

Treatment-emergent period: The treatment-emergent period is defined as the period of time from the date and time of the first dose of exicorilant through 30 days after the last dose of

study drug (exicorilant or enzalutamide whichever is later). The treatment-emergent period will be used in the summaries of treatment-emergent adverse events (TEAEs).

Baseline and postbaseline value: Unless otherwise specified, a baseline value will be defined as the most recent value on or before the first dose of exicorilant including PRO, QoL and baseline characteristics. In addition, pretreatment Cycle 1 Day 1 values could serve as baseline. A postbaseline value is defined as an assessment obtained after the first dose of exicorilant.

Baseline and postbaseline value for safety analyses: Unless otherwise specified, a baseline value for safety analyses is defined as the last value on or before the date/time of first dose of exicorilant for laboratory tests, vital sign assessments, and ECG data. A postbaseline value for safety analyses is defined as a measurement taken after the date/time of first dose of exicorilant. If multiple toxicity grades are present for the same date, the worst toxicity grade will be used in the summaries of toxicity grade by laboratory tests. For triplicate measurements of ECG, worst results will be used in the summaries presented by visit. For all other safety parameters, if multiple measurements are present for the same date, latest available value will be considered for summaries.

Last dose date: Date of last dose of exicorilant or enzalutamide (whichever is last) from the end of treatment – exicorilant and enzalutamide eCRFs.

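### The SAP keeps only a worst-of-three shift table for ECGs and, without declaring it, drops the protocol's summaries of ECG parameters and their change by time point

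*SAP*

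**What the plan says.** Protocol 9.5.6 groups ECG with laboratory tests and vital signs: "abnormal ECG values will be summarized overall and for each treatment regimen dose group by parameter, visit, and time" point. It asks for descriptive statistics that include change from baseline. A separate sentence adds shift tables from baseline to end of treatment. Protocol 6.3.4 collects ECGs in triplicate, with recordings before dosing and 2 hours after dosing on the on-treatment days.

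The SAP is narrower in three places. Section 4.2.1 gives laboratory tests and vital signs a change-from-baseline endpoint, but gives ECG only a shift. Section 7.2 sets the rule for triplicates: "For triplicate measurements of ECG, worst results will be used in the summaries presented by visit". Section 10.5 makes the physician responsible for "determining whether the ECG is normal, abnormal clinically significant, or abnormal not clinically significant". It then states that "All recorded results will be included in a listing" and that the "worst result of the triplicate readings at each visit will be summarized for each treatment arm as shift from Baseline". Section 13, which records changes from the protocol's analyses, covers only the treatment-emergent and baseline definitions.

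**The concern.** A three-level overall call shows that something on the tracing was judged abnormal. It does not show which interval changed, by how much, or whether the change followed the dose. The trial collects triplicates timed around dosing, which is more than such a call needs. The protocol also pays some attention to QT. Exclusion criterion 8c covers "Recent history of or risk factors for torsades de pointes, including marked baseline prolongation of QT interval", with repeated QTcF above 450 ms as an example, and Appendix C asks for QT-prolonging drugs to be replaced or stopped where possible.

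Under Protocol 5.6 the recommended dose takes overall tolerability into account. If the ECG output is only a shift table, the Data Review Committee and the study report have no specified table of QTcF or its change. Anyone comparing the report with the protocol would also find a planned analysis missing without explanation.

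**Working it through.** This is a comparison of texts; there is no planned figure to reproduce.

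**1. Side by side**

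| Feature | Protocol 9.5.6 | SAP 4.2.1, 7.2, 10.5 |
|---|---|---|
| Descriptive statistics with change from baseline | Yes, for abnormal ECG values | None for ECG |
| Shift table | Yes, in addition | Yes, the only summary |
| By ECG parameter | Yes | No interval named |
| By time point within visit | Yes | Per visit; pre-dose and 2-hour handling not stated |
| Grouping | Dose group and overall | Treatment arm |
| Combining triplicates | Not stated | Worst of three |

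The grouping matters because SAP 8.8 describes Segment 1 as three cohorts, not arms. SAP 10.3 and 10.4 keep numeric values and changes, by dose group or arm and overall, for laboratory tests and vital signs. The reduction is therefore specific to ECG.

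**2. Which variable is shifted.** SAP 10.5 does not say outright. The investigator's call is the only ECG result scale the SAP names, and it comes immediately before the shift rule, so it is the natural reading. It remains an inference.

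**3. How a QTcF increase could still be seen.** There are three routes: the shift table, if the investigator's call changes; the adverse event tables in SAP 10.1, if it is reported as an event; and the patient listing. None of these is a summary of the interval or its change.

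**4. Worst of three for a numeric interval.** For three independent normal readings, the expected maximum exceeds the mean by 3/(2√π) = 3/3.545 = 0.846 within-occasion SDs. The documents give no such SD. Assuming 5, 8 or 10 ms, the excess is 0.846 × 5 = 4.2 ms, 0.846 × 8 = 6.8 ms or 0.846 × 10 = 8.5 ms. It would largely cancel in a change if baseline were also a worst of three, but not in the values themselves. The rule suits a categorical call and not an interval.

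**5. ECG days against dose in Segment 2.** Titration begins on Cycle 1 Day 16 (Protocol 5.4.2).

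- Protocol 6.3.4 and 7.3 place on-treatment ECGs at Cycle 1 Day 1, Cycle 1 Day 15 and Cycle 3 Day 1, without restricting the last.
- Note h of the overall schedule (Protocol Table 16) and SAP 10.5 limit Cycle 3 Day 1 to Segment 1.

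Under the second version, Segment 2 has scheduled on-treatment ECGs only on Days 1 and 15. Both fall before Day 16, when every patient in both arms is planned to take 240 mg. The remaining scheduled ECG is at the visit 30 days after end of treatment.

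**The case against.** The best defence is that this is a small documentation gap. Its main arguments, and what stands of each:

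- **The protocol promises less than it seems to.** It says abnormal ECG values, so a QTcF rise within normal limits is not clearly covered there either. This stands: a reader might infer that the protocol analysis would have shown any QTcF effect and its size, and the text does not support that. The by-parameter and by-time-point change summary is still planned and still absent.
- **An increase is not invisible.** This stands. It would be wrong to say that a QTcF increase could appear in no summary, given the shift and adverse event tables.
- **An abnormal baseline does not block a shift.** This stands. With three levels, a patient can move from abnormal but not clinically significant to clinically significant.
- **Pre-dose and 2-hour readings may not be merged.** This stands as an ambiguity. SAP 7.2 defines safety baseline by date and time of first dose, which separates the two triplicates on Cycle 1 Day 1. For later visits the wording is open.
- **QT is not an identified risk.** Protocol 1.6 names none for CORT125281, and 450 ms is only an example within an exclusion criterion. This lowers the urgency but does not remove the planned analysis.
- **The table could not inform the titrated doses.** Under note h and SAP 10.5 this is right, so a reader should not infer that better ECG tables alone would reveal an effect at 280 or 320 mg. It adds a second item to reconcile and does not excuse the first.
- **The interval values may not exist in the database.** Protocol 6.3.4 describes interpretation of the tracing and its retention at the site. Neither document shows that intervals are entered on the case report form. This stands and governs the cost.

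**Conclusion.** The SAP makes an undeclared reduction of the protocol's ECG analysis and should be corrected. Of the two kinds of ECG summary planned, only the shift table remains. No specified summary contains QTcF, any other interval, or its change from baseline. The primary DLT analysis is not defined from this table; the loss is in describing tolerability.

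The conclusion rests on reading SAP 10.5 as shifting the investigator's call. If another ECG result was meant, the SAP does not name it, and the change-from-baseline summary is missing either way. I put no figure on a missed QT effect, because the documents give no QTcF mean, variability or expected change; the millisecond range for the worst-of-three rule uses assumed SDs. Counts above QTcF thresholds appear in neither analysis plan, so their absence is not a departure from the protocol.

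**What to change.** In SAP 4.2.1, 7.2 and 10.5:

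- Add descriptive summaries of the recorded ECG parameters, including QTcF, and their change from baseline. Present them by dose group or arm and overall, at each visit, with pre-dose and 2-hour time points separate.
- Use the mean of each triplicate for numeric intervals, and apply the worst-of-three rule only to the categorical call.
- Name the variable in the shift table, and keep that table.
- State whether the summaries cover all values or only abnormal ones. A change from baseline restricted to abnormal values would be selective.

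Categorical QTcF counts are an optional addition.

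First confirm that interval values are in the database. If they are, the cost is SAP wording and one or two tables, with no new procedure. If they are not, declare and justify the departure in Section 13.

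Separately, reconcile Protocol 6.3.4 and 7.3 with note h of the overall schedule and SAP 10.5 on the Cycle 3 Day 1 ECG. State in the SAP which Segment 2 dose levels the scheduled ECGs can describe.
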